We propose to carry out an open label safety and efficacy trial of oral weekly GC steroids in patients with BMD and LGMD subtypes. Subjects will be recruited based on age, molecular diagnosis of BMD and LGMD subtypes, and willingness to participate. Both ambulatory and nonambulatory subjects will be included. Subjects will be excluded if they have diabetes mellitus, full time ventilator use, or severely compromised cardiac function, including symptoms referable to heart failure. Subjects must provide consent.

Subjects will be asked to take weekly GC oral prednisone dosed based on weight (1mg/kg for patients who weigh less than or equal to 70 kg and 0.75 mg/kg for patients who weigh more than 70 kg). Subjects will also be instructed to take their weekly prednisone on Mondays after their last meal between 7 and 9 PM. Prior to initiation, subjects will provide a blood sample for baseline screening including serum chemistries, HgbA1-C, creatine kinase, and lipid panel (HDL, LDL, triglycerides, and total cholesterol) and for exploratory biomarkers. Subjects will also provide a urine sample to analyze changes in metabolic biomarkers that are excreted. Subjects will have a physical exam and medical record review. Subjects will have strength testing and complete 10 meter timed run test in addition to a 6 min walk test (if ambulatory). Subjects will be asked to complete quality of life questionnaire. At 6 months, subjects will be evaluated with physical exam, strength testing, spirometry, 10 meter timed run test and 6 min

walk test (if ambulatory), blood draw for serum chemistry, HgbA1-C, creatine kinase, lipid panel and for exploratory biomarkers. Subjects will also provide a urine specimen to be analyzed for any changes in excretion of metabolic markers as an exploratory endpoint. Subjects will be asked to complete a quality of life questionnaire. An MRI/ MRS will be performed before starting GC oral prednisone and at 6 months.

STUDY ENDPOINTS:

Primary Outcome: Safety

Safety monitoring:

- Comprehensive chemistry panel, hemoglobin A1C, CK, lipid panel at screening and after 6 months of GC steroid dosing
- FVC (sitting, supine) at screening and at 6 months
- Phone calls to each patient each month to determine their state of health and study drug compliance.

Secondary Outcomes: Change in MRI muscle mass, improved muscle performance, improved quality of life, blood and urine metabolic biomarker changes.

Functional Assessments

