- NSAD (Northstar Assessment for Dysferlinopathy)—AMB
- 6 min walk test and 10 meter timed run test, if patient ambulatory
- PUL (Performance of Upper Limb)
- Brooke Scale
- Vignos Scale

Strength assessments

- MMT MRC

Patient Reported Outcome Measures

- PROM: ACTIVLM
- Quality of life questionnaire

Blood and urine for exploratory biomarkers

Imaging

- MRI/ MRS of leg and arm muscles to measure muscle volume, T2 value and fat fraction
- DEXA scan at screening and at 6 months

Outcome measures:

- Comparing MRI/MRS changes the leg and arm muscles at screening and 6 months
- Change in 6 min walk test and 10 meter timed run test for ambulatory patients
- Change in strength assessment
- Change in FVC measurements

Strength assessment:

- MRC scale: Shoulder abduction, elbow flexion, knee extension and knee flexion, hip flexion, foot dorsiflexion.
- Grip strength (Jamar dynamometer)

- Hand held dynamometry

Functional testing:

- Lift arm above head
- Lift arm above head using 50g/100g/200g/500g weight
- Bring arm to the mouth
- Bring weight to mouth using 50g/100g/200g/500g weight

STUDY INTERVENTION(S) / INVESTIGATIONAL AGENT(S):

Oral prednisone is a synthetic glucocorticoid that is FDA-approved medication for the treatment of various inflammatory and allergic conditions.

In this study, subjects will be asked to take weekly GC oral prednisone, dosed based on weight (1mg/kg for patients who weigh less than or equal to 70 kg and 0.75 mg/kg for patients who weigh more than 70 kg). Subjects will be instructed to take weekly prednisone on Mondays after their last meal between 7 and 9 PM. Study drug, oral prednisone, will be stored under the secure and controlled environment of the Investigational Drug Pharmacy at Northwestern Memorial Hospital. The Investigational Drug Pharmacy will follow its current SOP regarding the storage and handling of investigative drugs. The study drug will be dispensed from the Pharmacy and administered to subjects once they have signed informed consent, passed screening, on Day 0 of their treatment. Subjects will return home with 6 months of study drug treatment. They will be educated on dosing, storage, and return of unused study drug by the study staff. Subjects will be contacted on a monthly basis to assess medication and dosing adherence. They will be asked to confirm their medication and the dosing instructions and re-educated if not adhering.

PROCEDURES INVOLVED:

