A member of the study team (physical or occupational therapist) will complete the following functional assessments: Northstar Assessment for Dysferlinopathy (NSAD) –AMB, 10 meter timed run test and 6-minute walk test if the patient is ambulatory, performance of upper limb (PUL) evaluation, Brookes and Vignos scales. A member of the study team will also collect the strength assessment, MMT MRC.

Subjects will be asked to complete two questionnaires; ACTIVLM and a Quality of Life Questionnaire.

The subject will also complete a bone density (DEXA) scan at Northwestern Memorial Hospital.

An MRI will be conducted at the Center for Translational Imaging at Northwestern University within 2 weeks before or after the subject’s final visit. No contrast will be administered.

An overview of the study assessments may be found in Table 1.0 below:

| | Screening (D0-2M) | Day 0 | M6 +2 wks |
|--------------------------------------|-------------------|-------|-----------|
| Informed Consent | X | | |
| Demographics | X | | |
| Vital Signs | X | X | X |
| Weight and Height | X | X | X |
| Medical History | X | X | X |
| Concomitant Medications | X | X | X |
| Genetic mutation Confirmation | X | | |
| Review EKG* | X | | |
| Review Echo** | X | | |
| Safety Monitoring Labs*** | | X | X |
| Forced Vital Capacity (FVC) | | X | X |
| NSAD | | X | X |
| 6-min Walk Test / 10 m Run | | X | X |
| Performance of Upper Limb | | X | X |
| Brooke Scale | | X | X |
| Vignos Scale | | X | X |
| MMT MRC | | X | X |
| Grip Strength | | X | X |
| ACTIVLM | | X | X |
| Quality of Life Questionnaire (SF36) | | X | X |
| MRI/MRS | | X | X |
| DEXA Scan | | X | X |
| Study Drug Dispensation | | X | |
| Review of Adverse Events | | | X |

Table 1.0: Schedule of Assessments from Screening, Day 0, and Month 6

* EKG – Results within 2 months of study initiation accepted

**Echo – Results within 6 month of study initiation accepted

*** Comprehensive chemistry panel, hemoglobin A1C, CK, lipid panel

SHARING RESULTS WITH PARTICIPANTS

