Results of investigational diagnostic tests, and incidental findings, will be shared with the subjects through the MyChart patient portal. Once the laboratory samples are drawn and analyzed by the Northwestern Memorial Hospital Main Laboratory, the results will be posted to MyChart. If the results are abnormal and clinically significant, the Principal Investigator will notify the subject about further testing and treatment. Furthermore, the Principal Investigator will contact and inform the subject's primary care physician.

Results from questionnaires, functional assessments, blood / urine exploratory biomarkers, DEXA, and MRI imaging will not be shared with the patient.

STUDY TIMELINES

The study team will screen and enroll subjects for a period no longer than 1 year from IRB approval.

Screening will occur at one clinic visit that will last no more than 2 hours. If subjects have not had a MRI within the previous 6 months, they will return for a MRI (1 hour). Similarly, if subjects have not had a DEXA scan within the previous 6 months, they will return for a DEXA scan (1 hour).

Enrolled subjects will participate in the study for 6 months from their first dosing (Day 0). Subjects will schedule their MRI and DEXA scan on the final day of the study. If subjects are unable to complete a MRI or DEXA on that day, they will return to complete the required procedure within the next 2 weeks.

The investigators estimate the study's primary analyses will be completed by December 2019.

INCLUSION AND EXCLUSION CRITERIA

Inclusion criteria (Collected at screening):

1. Patients with Becker muscular dystrophy or LGMD2A (CAPN3), LGMD 2B (DYSF), LGMD 2C (SGCG), LGMD2E (SGCB), LGMD2F (SGCD), LGMD 2I (FKRP), LGMD (ANO5). Genetic mutation or muscle biopsy staining required to confirm genetic subtype
2. Ages 18-65 years
3. EKG without evidence of prior infarct or atrial fibrillation done within 2 months of study initiation.
4. Echocardiogram with LVEF >25% done within 6 months of study initiation.
5. Stable medications (same medication and dose) for the previous 3 months
6. Stable pulmonary status for the previous 6 months (No change in FVC by more than 20% in the past 6-months)

Exclusion criteria (Collected at screening):

1. Diabetes
2. BMI>35 kg/m²
3. Cardiac transplantation
4. Myocardia Infarct in the past 2-years from screening
5. Any history of tuberculosis
6. Untreated or uncontrolled (medication and/or dose change in previous month from screening) hypertension

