Some people cannot have an MRI because they have certain types of metal in their body. For instance, if you have a heart pacemaker, artificial heart valves, metal implants such as metal ear implants, bullet pieces, chemotherapy or insulin pumps or any other metal such as metal clips or rings, you cannot have an MRI. During this test, subjects will lie in a small closed area inside a large magnetic tube. Some people are scared or anxious in small places (claustrophobic). The MRI scanner makes loud banging noises while taking a measurement, so either ear plugs or specially designed headphones will be used to reduce the noise.

Risks from DEXA bone scans

Procedures such as CT scans, X-rays and/or radioactive drugs will be used during this research study to see how subjects are doing. The cumulative radiation exposure from these tests is considered small and is not likely to adversely affect subjects or their disease. However, the effects of radiation add up over a lifetime. It is possible that having several of these tests may add to subjects' risk of injury or disease. When deciding to enter this study, subjects will think about their past and future contact with radiation. Examples of contact with radiation include x-rays taken for any reason or radiation therapy for cancer treatment.

Background radiation is present on Earth (soil, air, water, food) and also includes cosmic radiation. Exposure to radiation from natural sources is a feature of everyday life. Your

participation in this study will involve additional exposure to radiation. The radiation dose received for one DEXA scan is approximately equal to 4.5 days of background radiation.

The effective dose for one DEXA scan (lumbar spine and total hip) is 4 mrem. The total effective dose of all research related radiation procedures is 8 mrem.

POTENTIAL BENEFITS TO PARTICIPANTS

There may be benefit from participating in this research. Potential benefit may include increased strength and muscle mass.

DATA MANAGEMENT AND CONFIDENTIALITY

This is a pilot study to determine safety and tolerability of the intervention. All subjects will receive once weekly prednisone, and no placebo arm is planned for this study. Data will be compared between study entry and 6 months of once weekly steroids. The data from this study will be used to plan for a larger trial. In preclinical animal models, a 25% improvement in muscle strength and function was observed.

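### Read plainly, the Month 6 walk and run tests cover only subjects still ambulatory, so anyone who stops walking leaves two secondary change measures, normally shifting them towards benefit

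*Protocol*

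**What the plan says.** In the Protocol, PROCEDURES INVOLVED, the Month 6 subsection has a therapist do the "10 meter timed run test and 6-minute walk test if the patient is ambulatory". The Day 0 subsection carries the same phrase as its own instruction. BACKGROUND also lists both tests at 6 months with the same restriction in brackets.

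Under STUDY ENDPOINTS, Outcome measures, the endpoint is "Change in 6 min walk test and 10 meter timed run test for ambulatory patients". No time point is attached to that status, and the term is not defined.

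The population is mixed: "Both ambulatory and nonambulatory subjects will be included" (BACKGROUND). The number expected to be ambulatory is not given. Table 1.0 marks the walk and run at Day 0 and Month 6 with no condition.

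The comparison is before versus after: "Data will be compared between study entry and 6 months of once weekly steroids", and "no placebo arm is planned for this study" (both under DATA MANAGEMENT AND CONFIDENTIALITY). Muscle performance is a secondary outcome; the primary outcome is safety.

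**The concern.** Whether a subject can still walk at Month 6 is itself a result of the disease and possibly of the treatment. If that result decides who is tested, the worst outcome on the walk and run tests becomes a blank instead of a poor score. The change is then averaged over those who kept walking.

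Three features of this trial make that matter:

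- No control arm loses walkers in parallel, so nothing offsets the selection. The hypothesis in OBJECTIVES is improvement over the subject's own baseline.
- Worsening cannot be ruled out in advance. BACKGROUND cites a randomised trial of steroids in LGMD 2B with unfavourable outcomes in the treated group, and LGMD 2B is eligible here. The entry criteria set no minimum walking ability.
- The data are meant for planning a larger trial, so an inflated change would carry forward.

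**Working it through.** The protocol gives no walking distance, number ambulatory or rate of loss, so there is no figure of its own to reproduce. The check derives the shift and evaluates it over assumed ranges.

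**Symbols.** n = subjects ambulatory at Day 0; k = those who lose walking by Month 6; b = their mean Day 0 6-minute walk distance; c = mean change in the n - k who still walk. The sample size of 30 is the only one of these limits that the protocol states. All values below are assumptions.

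**Step 1, the formula.** If lost walkers are dropped, the mean change is c. If they stay in and score 0 m at Month 6, it is ((n - k)c - kb)/n. The difference is

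c - ((n - k)c - kb)/n = (k/n)(b + c).

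This is above zero when k is at least 1 and b + c is positive. It would be negative only if the remaining walkers declined, on average, by more than the lost walkers' mean Day 0 distance.

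**Step 2, size with c = 0.** Shift in metres for b = 100 / 200 / 300 m:

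| n | one loss | two losses |
|---|---|---|
| 15 | 6.7 / 13.3 / 20.0 | 13.3 / 26.7 / 40.0 |
| 20 | 5.0 / 10.0 / 15.0 | 10.0 / 20.0 / 30.0 |
| 30 | 3.3 / 6.7 / 10.0 | 6.7 / 13.3 / 20.0 |

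With no loss the shift is 0 in every row.

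**Step 3, can the sign change?** Take n = 20, c = +10 m and b = 250 m. One loss gives (19 × 10 - 250)/20 = -3.0 m. Two losses give (18 × 10 - 500)/20 = -16.0 m. Dropping the lost walkers gives +10 m in both cases. With a lower start of b = 50 m, one loss gives (19 × 10 - 50)/20 = +7.0 m, a shift of only 3 m with no change of sign. With c = +10 m, the one-loss shift is 160/25 = 6.4 m for n = 25 and b = 150 m, and 260/15 = 17.3 m for n = 15 and b = 250 m.

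**Step 4, chance of at least one loss.** This is 1 - (1 - p)^n. For n = 20 it is 18% at p = 1%, 33% at p = 2%, 64% at p = 5% and 88% at p = 10%. The protocol gives no p.

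**Step 5, the 10 m run.** Someone who cannot complete the run has no finite time, so a change in seconds cannot be scored. On the speed scale inability is 0 m/s, and the formula in Step 1 applies with b and c as speeds.

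**Step 6, what scoring zero does to the spread.** Assume 19 walkers with mean change +10 m and SD 40 m, plus one change of -250 m. The sum of squares is 18 × 40² + (19/20) × 260² = 28,800 + 64,220 = 93,020. Dividing by 19 gives a variance of about 4,896 and an SD of about 70 m. The variance is about three times the 1,600 among the walkers alone.

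**The case against.** The strongest reply is that the protocol never says ambulatory status is judged again at Month 6. The same phrase serves both visits, BACKGROUND and the outcome list use the word as a class of patient, and Table 1.0 schedules the tests without a condition. Nor does the protocol say that change is analysed only in observed pairs. Scoring of inability and the analysis set are commonly left to an SAP, which is not shown here.

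Part of this stands: the timing is partly an inference. But a condition written into a visit's own procedures is most naturally applied at that visit, and the outcome measure carries the same restriction. An SAP that scored lost walkers as zero would have to read past both. The point concerns what the protocol states, not a detail it omits.

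A second reply is that the loss is not invisible. The Vignos scale is done at Day 0 and Month 6 with no ambulatory condition, adverse events are reviewed at Month 6, and monthly calls ask about changes in physical health. This stands in full. A reader might infer that the plan hides a harm; the documents support only that the harm would be missing from the walk and run results.

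A third reply is that the size is wholly assumed and computed on a mean, which the protocol does not specify. That also stands. The sign change in Step 3 is an illustration, not a forecast.

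**Conclusion.** The concern holds in conditional form. Followed as written, the Month 6 condition and the restricted outcome measure remove a subject who stops walking from two secondary change measures, normally in the direction of benefit. If the mean is used, one loss shifts the 6-minute walk change by about 3 to 20 m, for 15 to 30 subjects ambulatory at Day 0, Day 0 distances of 100 to 300 m and no mean change in the others.

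Two stronger readings are not supported. A reader might conclude that the result is biased outright; it is not if nobody loses walking within 6 months, and the protocol gives no rate. A reader might also conclude that the bias can only run upwards; Step 1 shows that this is usual but not strictly true.

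The primary safety outcome is not affected, nor are the MRI, upper-limb, manual muscle testing, Vignos, FVC and quality-of-life measures. The change is worth making because it is cheap and there is no control arm to reveal the selection.

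**What to change.** - In the outcome measures, define the analysis set for both tests as subjects ambulatory at Day 0.
- In the Month 6 procedures, record inability due to loss of walking as 0 m for the 6-minute walk. Analyse the 10 m run as speed, with 0 m/s for inability. Keep this apart from a test missed for other reasons.
- Report the number of subjects who lose ambulation.
- Summarise by median change or a rank-based paired test.

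The cost is about one sentence in the Month 6 procedures and one in the outcome measures, with no extra tests. There are two downsides. A zero can raise the variance of a mean substantially, as Step 6 shows, which is the reason for the median or rank-based summary. The estimate will also be less favourable if anyone loses walking.

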This is an open label study that evaluates the safety and efficacy of oral weekly glucocorticoid steroids in patients with BMD and LGMD over 6 months. The study is comprised of three visits; screening to determine eligibility, initial dosing (Day 0), and final dosing (Month 6).

Screening

All subjects will be recruited to the study through the Muscular Dystrophy (MDA) Clinic at Northwestern Memorial Hospital. Prior to any study procedures, the study team will complete the full informed consent process with each patient. Upon obtaining informed consent, the study team will collect information from the patient including: demographics, vital signs, weight, height, medical history, concomitant medication, genetic mutation test results, EKG and Echocardiogram test results. If the subject does not have EKG or Echocardiogram results within the last 2 and 6 months, respectively, they will not be screened until they complete these two procedures as part of their standard of care. The principal investigator will review this information and determine whether the subject is eligible to participate in the study. If the subject is ineligible, he/she will be notified and continue to seek treatment through their treating physician.

Data will be retained in paper source materials by members of the study team at [name].

Day 0

Subjects will return to the MDA Clinic at Northwestern Memorial Hospital for the Day 0 procedures. If on a separate day from the screening visit, the study team will review concomitant medications, medical history, and collect vital signs with height and weight.

The following laboratory tests will be collected for safety purposes: A comprehensive chemistry panel, hemoglobin A1C, CK, and lipid panel. A blood and urine sample will be taken for exploratory biomarkers. Samples will be collected by members of the study team and processed by the Northwestern Memorial Hospital Main Laboratory. Records will be populated in the patient's medical charts and stored by members of the study team in the subject binders.

A member of the study team will also collect forced vital capacity in a sitting and supine position.

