7. A diagnosis of congestive heart failure
8. A diagnosis of chronic kidney disease
9. A diagnosis of untreated hypothyroidism
10. The patient is believed to be at high risk of osteoporosis by the primary investigator
11. Inability to provide consent
12. Prior oral glucocorticoid steroid use for > than one month during a subject's life.
13. Full time ventilator dependency
14. Heart failure symptoms or LVEF <25%
15. Orthopedic surgery within the prior year or upcoming elective orthopedic surgery within the 6-months from Day 0.
16. Inability to complete MRI (claustrophobia, metal implants)
17. Pregnant women at screening, women seeking to become pregnant, or men seeking to father a child within 6-months from Day 0 should not participate in this study.

PARTICIPANT POPULATION(S)

| Accrual Number: | Category/Group: (Adults) | Consented: Maximum Number to be Consented or Reviewed/Collected/Screened | Enrolled: Number to Complete the Study or Needed to Address the Research Question |
|-----------------|--------------------------|--|---|
| Total: | 50 adults | 40 adults | 30 adults |

RECRUITMENT METHODS

All subjects will be recruited through the Muscular Dystrophy (MDA) clinic at Northwestern Memorial Hospital. The MDA clinic is located in the [name] and is held on Wednesday mornings from 08:00-12:00.

Participants will be selected by the neurologists in the MDA clinic, primarily the Principal Investigator. They will be selected for screening based on their clinical exam, medical history, and willingness to participate in the study. The Principal Investigator will review the patient's medical chart to determine pre-eligibility. A member of the study team will conduct the informed consent process once pre-eligibility is confirmed by the Principal Investigator.

No external methods will be used for recruitment purposes.

COMPENSATION FOR PARTICIPATION IN RESEARCH ACTIVITIES

Subjects will not be compensated for participating in this study. Furthermore, subjects will not be reimbursed for expenses related to travel, lodging, or accommodation.

If patients become ill or are injured as a result of this study (medications, devices or procedures), they should seek medical treatment through their doctor or treatment center of choice. The subject should promptly tell his/her study doctor about any illness or injury.

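### A clinically significant DEXA result carries no duty to tell the subject or the primary care physician, and the gap is clearest at Month 6

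*Protocol*

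**What the plan says.** The Protocol section Sharing Results with Participants has two paragraphs.

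- The first opens with a general rule: "Results of investigational diagnostic tests, and incidental findings, will be shared with the subjects through the MyChart patient portal". It turns to laboratory samples: "Once the laboratory samples are drawn and analyzed by the Northwestern Memorial Hospital Main Laboratory, the results will be posted to MyChart". The next sentence sets the duty to act: "If the results are abnormal and clinically significant, the Principal Investigator will notify the subject about further testing and treatment". The paragraph ends by having the investigator inform the primary care physician as well.
- The second is a single sentence: "Results from questionnaires, functional assessments, blood / urine exploratory biomarkers, DEXA, and MRI imaging will not be shared with the patient".

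DEXA is planned at baseline and at 6 months (Study Endpoints; Procedures Involved; Table 1.0). On the closing scan, Study Timelines says: "Subjects will schedule their MRI and DEXA scan on the final day of the study". A subject who cannot manage that day has 2 further weeks. Risks to Participants includes loss of bone density among the glucocorticoid risks, while expecting much less risk with weekly dosing. Data Management and Confidentiality lists DEXA among the results that the study team takes from the hospital's electronic record.

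**The concern.** DEXA measures a harm that the protocol itself attributes to the study drug, in a trial whose primary objective is safety. Even so, the protocol treats it like a questionnaire score or an exploratory biomarker: the value is collected and withheld. An abnormal laboratory value leads to a call to the subject and contact with the physician. An abnormal bone density has no such route, and the protocol gives no reason for the difference.

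At stake is the care of individual subjects. Under the rule as written, a low or falling bone density on weekly prednisone could sit in the study binder with neither the subject nor the physician told. No endpoint, sample size or error rate depends on this.

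**Working it through.** The protocol states no figure on this point that could be reproduced. The check is a reading of the text, followed by a count.

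**1. Which results does the duty to notify cover?** The duty speaks of results that are abnormal and clinically significant. The sentence immediately before it concerns samples analysed by the hospital's main laboratory, so that is the natural reference. The following paragraph then names DEXA among the results that are not shared. In context, the duty covers laboratory results.

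**2. Does the opening sentence bring DEXA in?** It could do so in two ways.
- *As an incidental finding.* Bone density is what DEXA is meant to measure, so a low value is not incidental.
- *As an investigational diagnostic test.* In that case the first paragraph requires sharing and the second forbids it. The two contradict each other and still need reconciling.

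**3. Do other provisions fill the gap?**

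| Provision | Baseline scan | Month 6 scan |
|---|---|---|
| Exclusion 10: "The patient is believed to be at high risk of osteoporosis by the primary investigator" | Possible, at the investigator's judgement | Too late |
| Procedures Involved, Screening: "If the subject is ineligible, he/she will be notified and continue to seek treatment through their treating physician" | Only if the subject is found ineligible | Does not apply |
| Withdrawal for risk of harm, with advice on further testing and care | Discretionary, and only for a subject who is withdrawn | Too late |
| DEXA result in the electronic record | The team can see it; no duty to report | The same |
| Telling the physician (the bar names only the patient) | Allowed, not required | Allowed, not required |

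No row creates a duty to report a DEXA result. At Month 6 the only rows left are access without obligation and permission without obligation.

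**4. How many scans?** Participant Population(s) gives, in its total row, "50 adults | 40 adults | 30 adults". The 40 stands under the maximum to be consented and the 30 under the number to complete. Each completer has 2 DEXA results, one at baseline and one at Month 6.
- Month 6 reports: 30 × 1 = 30.
- Baseline reports: 30 if only completers have one, up to 40 if every consented adult does.
- Total: 30 + 30 = 60, up to 40 + 30 = 70.

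These are counts of reports, not of subjects harmed. The protocol gives no rate of clinically significant DEXA findings, so the second number cannot be derived.

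**5. MRI.** The same sentence withholds MRI results. The text does not say whether an incidental MRI finding follows the rule on incidental findings or the rule on non-sharing. This is a smaller point of wording.

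**The case against.** The strongest reply is that the section can be read more generously. The duty to notify does not contain the word laboratory. The non-sharing sentence groups DEXA with research measurements, which suggests a policy on routine return of values rather than silence about abnormal ones. The practical risk is also limited. Subjects come from the clinic where the principal investigator recruits, they are seen at routine care visits, and the DEXA result is in the hospital record. Exclusion, notice of ineligibility and withdrawal offer some cover at baseline. The protocol expects side effects of 6 months of weekly dosing to be low in risk, brief and reversible. The upper count of 70 is weakly supported: Table 1.0 places DEXA at Day 0, so subjects who fail screening need not be scanned, and a scan accepted from the previous 6 months may predate the study. Finally, the consent form might address the matter and is not shown.

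Much of this stands as a limit on size. The baseline gap is partly covered, 70 is only an upper bound, and the MRI point is minor. None of it removes the main point. The generous reading is less natural than the laboratory-only one and leaves two paragraphs in conflict. Access to a result is not a duty to act on it. The expectation of low risk rests on animal work and limited human data, and this pilot is meant to test safety. Whatever the consent form says, the protocol sentence would still need to agree with it.

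**Conclusion.** The concern holds. The protocol withholds DEXA results from the subject without exception and places no duty on anyone to report a clinically significant one. The gap is partial at baseline and clear at Month 6, when 30 scans are expected if 30 subjects complete. Across both time points there are about 60 reports, at most 70. That range assumes 30 completers, between 30 and 40 baseline scans, and that an accepted earlier scan counts as a report to review. The conclusion also rests on reading the duty to notify as limited to laboratory results; on the wider reading the fault is a contradiction, and the same correction is needed. How many subjects would have a significant finding is unknown. The point is worth correcting for patient safety and has no bearing on the endpoints or the analysis.

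**What to change.** Amend the second paragraph of Sharing Results with Participants in two sentences.

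- State that routine research values from DEXA and MRI are not returned, but that the Principal Investigator reviews any clinically significant DEXA result, at baseline or Month 6, and reports it to the subject and the primary care physician by the route already used for abnormal laboratory results.
- State that an incidental MRI finding that comes to the study team's attention follows the existing rule on sharing incidental findings. This is a clarification only.

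The cost is a brief investigator review of about 60 DEXA reports, at most 70, which the team already obtains from the electronic record. No scan or visit is added. No clinical MRI read is added either: the de-identified images go to an outside university for interpretation, and the protocol describes no clinical read. The consent form may need a matching change.
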